1	2	1	-1	-12:00	20:00	Admission to trial site ¹⁰	x ⁵					x
			-1:30	06:30	Allocation to treatment		x ²	x ²		x ²	x ²	x ²
			0:00	08:00	50 mg BI 409306 p.o.							
			0:10	08:10		x						
			0:20	08:20		x						x
			0:30	08:30	0.1 mg BI 409306 i.v.	x ⁸			▲			
			0:35	08:35			x					
			0:45	08:45		x	x					
			0:50	08:50			x					
			1:00	09:00		x ⁹	x ⁹		+			
			1:10	09:10			x					
			1:20	09:20		x	x			x	x ⁷	
			1:30	09:30			x					
			1:45	09:45		x	x					
			2:00	10:00	240 mL fluid intake	x	x			x	x	x
			2:30	10:30		x	x					
			3:00	11:00		x	x					
			3:30	11:30		x	x					
			4:00	12:00	240 mL fluid intake, thereafter lunch ³	x	x			x	x	
			5:00	13:00		x	x					
			6:00	14:00		x	x					
			7:00	15:00		x	x					
			8:00	16:00	Snack (voluntary) ³	x	x					
			9:00	17:00		x	x					
			10:00	18:00		x	x					
			11:00	19:00	Dinner						x	x
			12:00	20:00		x	x				x ⁷	
EOT	3	2	n.a.	n.a.	End of trial (EOT) examination ⁴	x ⁴				x ⁴	x ⁴	x ⁴

Proprietary confidential information © 2018 Boehringer Ingelheim International GmbH or one or more of its affiliated companies

1. Subject must be informed and written informed consent obtained prior to starting any screening procedures. Screening procedures includes physical examination, check of vital signs, ECG, safety laboratory (including drug screening), demographics (including determination of body height and weight, smoking status and alcohol history and pregnancy test in women), relevant medical history, concomitant therapy and review of inclusion/exclusion criteria. Pharmacogenetic samples will be collected if needed
2. The time is approximate; the procedure is to be performed and completed within 3 h prior to (oral) drug administration.
3. If several actions are indicated at the same time point, the intake of meals will be the last action.
4. End of trial examination includes physical examination, vital signs, ECG, safety laboratory including pregnancy test in women, recording of AEs and concomitant therapies

Date of EOT coincides with day 2 of visit 2. All EOT activities take place *after* the formal discharge from the trial site. Exception: blood for the EOT safety lab is taken in the context of the 24:00 hours post-dose sampling to avoid two separate punctures

5. Only urine drug screening and alcohol breath test, and pregnancy test in women.
6. AEs and concomitant therapies will be recorded throughout the trial, but will be specifically asked for at the time points indicated in the [Flow Chart](#) above.

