 - The investigator does not need to actively monitor the subject for AEs but should only report related SAEs and related AESIs of which the investigator may become aware of by any means of communication, e.g. phone call. Those AEs should, however, not be reported in the CRF.

Figure 5.2.2.2: 1 Collection of AEs and AESIs

The REP refers to the oral drug administration. The REP of the BI 409306 (13-C/15-N) is considered to be negligible. Therefore, all AEs that occur through the treatment phase and throughout the REP will be considered as on treatment (without differentiation of intravenous or oral administration); please see Section [7.3.3](#). Events that occur after the REP until the end of trial examination will be considered to be follow-up events.

AE reporting to sponsor and timelines

The Investigator must report SAEs, AESIs, and non-serious AEs that are relevant for the reported SAE or AESI, on the BI SAE form via fax immediately (within 24 hours) to the sponsor's unique entry point (country specific contact details will be provided in the ISF). The same timeline applies if follow-up information becomes available. In specific occasions the Investigator could inform the sponsor upfront via telephone. This does not replace the requirement to complete and fax the BI SAE form.

Upon receipt of any further information relevant to the reported AEs, the investigator is to provide a follow-up SAE form to the sponsor. For follow-up information, the same rules and timelines apply as for the initial information.

Information required

For each AE, the investigator should provide the information requested on the appropriate eCRF pages and the BI SAE form, if applicable.

The following should also be recorded as an (S)AE in the CRF and on the BI SAE form (if applicable):

- Worsening of the underlying disease or of other pre-existing conditions
- Changes in vital signs, ECG, physical examination, and laboratory test results, if they are judged clinically relevant by the investigator

Proprietary confidential information © 2018 Boehringer Ingelheim International GmbH or one or more of its affiliated companies

If such abnormalities already pre-exist prior to trial inclusion they will be considered as baseline conditions.

All (S)AEs, including those persisting after the individual subject's end of trial, must be followed up until they have resolved, have been sufficiently characterised, or no further information can be obtained.

Pregnancy

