7.3.3 Safety analyses

Safety will be assessed for the endpoints listed in Section [5.2.1](#). All treated subjects (that is, all subjects who received at least one dose of study drug), will be included in the safety evaluation. Safety analyses will be descriptive in nature and will be based on BI standards.

The analyses will be done by 'treatment at onset'.

Treatments will be compared in a descriptive way. Tabulations of frequencies/proportions will be used for the evaluation of categorical (qualitative) data, and tabulations of descriptive statistics will be used to analyse continuous (quantitative) data.

Measurements (such as vital signs or laboratory parameters) or AEs will be assigned to treatments (see Section [4.1](#)) based on the actual treatment at the planned time of the measurement or on the recorded time of AE onset (concept of treatment emergent AEs).

Therefore, measurements planned or AEs recorded prior to first intake of trial medication will be assigned to 'screening', those between first trial medication intake until end of the residual effect period (see Section [5.2.2.2](#)) will be assigned to the treatment period. Events after the residual effect period but prior to next intake or end of trial examination will be summarized as 'follow-up'. These assignments including the corresponding time intervals will be defined in detail in the TSAP.

Adverse events will be coded using the Medical Dictionary for Regulatory Activities (MedDRA). Frequency, intensity and causal relationship of AEs will be tabulated by treatment, primary system organ class and preferred term. SAEs and other significant AEs (according to ICH E3), and AESIs will be listed separately (see Section [5.2.2.1](#)).

Proprietary confidential information © 2018 Boehringer Ingelheim International GmbH or one or more of its affiliated companies

Laboratory data will be compared to their reference ranges. Values outside the reference range will be flagged. Additionally, differences from baseline (screening measurements) will be evaluated.

For vital signs, the differences from baseline (last value before oral drug administration) will be evaluated.

Relevant ECG findings will be reported as AEs.

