6. GENERAL ANALYSIS DEFINITIONS

6.1 TREATMENTS

For basic study information on investigational products, assignment of treatments, and selection of doses, please see CTP, Sections 3 and 4.

The study will be performed as a non-randomised, open-label, single arm, single period trial with 2 treatments (T and R).

In total, it was planned to assign up to 12 healthy male and female subjects (6 subjects with CYP 2C19 non-PM status and up to 6 subjects with 2C19 PM status).

For details of dosage and formulation see Table 6.1: 1 and Table 6.1: 2 below:

Table 6.1: 1 Treatments and labels used in the analysis of AEs, safety laboratory data and vital signs as well as demographics

Treatment	Short label
A BI 409306 50mg tab + 0.1mg i.v.	BI tab + iv

Table 6.1: 2 Overview of treatments for intra-individual comparison

Treatment	Short label
T BI 409306, 50 mg tablet, qd	BI 50mg tab
R BI 409306 (C-13/N-15), 0.1 mg/mL i.v. solution 0.1 mg, qd	BI 0.1mg iv

The following separate study phases will be defined for the analyses of AEs:

- **Screening** (ranging from 0:00 h on day of informed consent until first administration time of study drug)
- **On treatment** (including residual effect period (REP);
- **Follow-up** (ranging from end of on treatment phase until 0:00 h on the day after trial termination date)

Displays of AEs will be presented without differentiation of intravenous or oral administration during on treatment phase.

Two types of AE displays will be provided in the report:

A) Section 15.3 and Appendix 16.1.13.1.8 (for ClinicalTrials.gov and EudraCT only) of the CTR displays:

In these displays, the on treatment phase will be analysed (labelled with the name of the study treatment (short label)). Screening and follow-up periods will not be included in this analysis.

B) Section 15.4 and Appendix 16.1.13.1.8 (except for ClinicalTrials.gov and EudraCT) of the CTR displays:

- Screening
- On treatment (labelled with the name of the study treatment (short label))
- Follow-up

In Section 16.1.13.1.8 AE tables, the following totals will be provided in addition:

- a total over all study phases ("Total")

Tables of vital signs and laboratory values will present results by the above mentioned on treatment phase.

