For detailed information on the handling of the treatments in the O*C views refer to Technical TSAP ADS plan. In particular, AEs will be counted for treatment if they occur up to the end of the residual effect period (REP) of 24 hours after oral administration.

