All adverse events occurring before first drug administration will be assigned to 'screening', those between intake of trial medication and end of the 24-hour REP will be assigned to treatment ('on treatment'). AEs occurring after the REP but prior to termination date will be assigned to 'follow-up'.

For more detail see the TSAP ADS plan.

According to ICH E3 (9), AEs classified as 'other significant' need to be reported and will include those non-serious and non-significant adverse events with

- (i) 'action taken = discontinuation' or 'action taken = reduced', or
- (ii) marked haematological and other lab abnormalities or lead to significant concomitant therapy as identified by the Clinical Monitor/Investigator at the Report Planning Meeting.

An overall summary of AEs (including AESIs) will be presented.

The frequency of subjects with AEs will be summarised by treatment (BI tab + iv), primary system organ class (SOC) and preferred term (PT). Separate tables will be provided for subjects with other significant AEs according to ICH E3 (9), for subjects with serious AEs, for subjects with drug-related AEs, for subjects with drug related serious adverse events and for subjects with AESIs.

The SOC and PTs will be sorted by frequency. The MedDRA version number will be displayed as a footnote in the respective output.

In addition, frequencies of subjects with non-serious AEs that had an incidence of > 5% for at least one treatment will be summarised by treatment, primary SOC and PT.

For disclosure of adverse events on EudraCT, additional information not included in a standard AE analysis will be performed. The following three entries will be created:

- Adverse Events per arm for disclosure on EudraCT
- Non-serious Adverse Events for disclosure on EudraCT
- Serious Adverse Events for disclosure on EudraCT

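### Does the SAP end the adverse-event follow-up phase at two different times?

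*SAP*

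**What the plan says.** **Where the rule is delegated.** Protocol 7.3.3 states "Events after the residual effect period but prior to next intake or end of trial examination will be summarized as 'follow-up" and then hands the detail over: "These assignments including the corresponding time intervals will be defined in detail in the TSAP". Protocol 5.2.2.2 puts it as "Events that occur after the REP until the end of trial examination will be considered to be follow-up events".

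**Where the rule is set.** SAP 6.1 lists three phases for the AE analysis: screening, on treatment and follow-up. It defines follow-up as "ranging from end of on treatment phase until 0:00 h on the day after trial termination date". It counts AEs for treatment "up to the end of the residual effect period (REP) of 24 hours after oral administration".

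**Where the rule is repeated.** SAP 7.8.1 describes the same three phases in running text and closes with "AEs occurring after the REP but prior to termination date will be assigned to 'follow-up". The next line sends the reader to the ADS plan for detail.

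**Timing of the last visit.** Footnote 4 of the protocol's Flow Chart says "Date of EOT coincides with day 2 of visit 2" and "All EOT activities take place *after* the formal discharge from the trial site". It makes an exception for the EOT safety blood, which it links to a sample 24 hours after dosing. The last timed row of the flow chart as given is 12:00. The EOT row carries no planned time.

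**The concern.** The protocol leaves the time intervals to the SAP, so the SAP should give one answer, and its two sections differ. SAP 6.1 includes the whole termination day. SAP 7.8.1, taken word for word, stops before that day begins. In this trial the residual effect period (REP) ends on Day 2 and the EOT examination is also on Day 2, so the literal SAP 7.8.1 window is empty.

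Events in that window are possible by design. Subjects stay at least 24 h after oral dosing (Protocol 6.2.2), and the EOT ECG, vital signs and physical examination follow discharge. A clinically relevant finding there becomes an AE. Such an AE is follow-up under SAP 6.1 and has no phase under a literal SAP 7.8.1. If two programmers followed the two sections, the Section 15.4 displays and the all-phase total in the appendix could differ.

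The laboratory draw seems to add a second difficulty. It is the only scheduled safety panel after dosing, its nominal time coincides with the end of the REP, and the sample it is tied to has no row in the flow chart.

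**Working it through.** The plan states no figure to reproduce. The check is clock arithmetic followed by a comparison of sections.

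**Inputs**
- Oral dose: about 08:00 on Day 1 (Flow Chart, approximate clock time).
- REP: 24 h after oral dosing (SAP 6.1 and 7.8.1).
- Termination date: taken as the EOT date, Day 2 (assumption; the EOT date is from footnote 4).

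**Start of follow-up**
- 08:00 Day 1 + 24 h = 08:00 Day 2, the same in both SAP sections.

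**Length of follow-up, termination on Day 2**
- SAP 6.1: 0:00 Day 3 − 08:00 Day 2 = 16 h.
- SAP 7.8.1, literal: 0:00 Day 2 − 08:00 Day 2 = −8 h, so 0 h.
- SAP 7.8.1, read as including the termination date: 16 h, identical to SAP 6.1.

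**Sensitivity**
- Assumed dosing between 07:00 and 10:00: 17 h to 14 h under SAP 6.1, and 0 h under literal SAP 7.8.1 throughout.
- Assumed termination on Day 3: 40 h against 16 h, a gap of 24 h. This departs from the scheduled Day 2 visit.

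**What part of the 16 h can hold an AE**
- Protocol 5.2.2.2 has AEs entered in the CRF up to the subject's end of trial. After that, only related serious events and related events of special interest that the investigator happens to learn of are reported, and not in the CRF.
- The hours from the EOT examination to midnight therefore add no CRF events. The interval that matters is REP end to EOT examination.
- Over that interval the SAP 6.1 midnight cut-off and the cut-off in Protocol 5.2.2.2 at the EOT examination select the same CRF events.

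**AE dated to the EOT laboratory draw**
- Protocol 7.3.3 assigns AEs by recorded onset time and reserves planned time for measurements.
- SAP 6.1 and 7.8.1 put onsets up to the end of the 24 h REP on treatment, and SAP 7.8.1 puts later onsets in follow-up.
- If the ±45 min window of Protocol 6.1 applies, the draw falls between 24:00 − 0:45 = 23:15 h and 24:00 + 0:45 = 24:45 h after dosing. An AE with onset at 23:15 h is on treatment and one at 24:45 h is follow-up, so the rule gives one phase in each case.
- Laboratory values are summarised by visit, screening against post examination (SAP 7.8.2), so the boundary does not affect them.

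**Outputs under either wording**
- Section 15.3 and the registry displays use the on-treatment phase only, so they are the same.
- Laboratory summaries and the individual listings in Appendix 16.2 are the same.
- Only Section 15.4 and the all-phase appendix total could differ, and only if the literal SAP 7.8.1 wording were programmed.

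**The case for a change.** The best case for acting is that the repair is nearly free. It would take one sentence in SAP 7.8.1, a definition of termination date and a corrected footnote. The protocol gives the SAP the task of fixing these intervals, so conflicting SAP sentences are not cured by pointing to an ADS plan that is not available here. Findings at the EOT examination are planned after the REP, so the affected window is not hypothetical.

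Part of this stands. The two sentences do differ, the termination date is not defined in the text given, and footnote 4 refers to a sample that the flow chart, as extracted, does not show.

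The harm does not follow. SAP 6.1 is the section that defines the phases, it gives an explicit clock time, and it requires a follow-up display in Section 15.4. An analyst who has that definition would not let a looser restatement turn a required phase into one that ends before it starts. If an AE did end up without a phase, it would still appear in the Appendix 16.2 listings, where at most 12 subjects make it easy to spot. The laboratory argument also fails, because the phase of such an AE is settled by its recorded onset. Assigning it by the planned time of the draw would contradict Protocol 7.3.3.

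**Conclusion.** This is a loose restatement and a clerical slip, and neither needs a change to the plan. The nominal difference is 16 h against 0 h, but it arises only under a literal reading that makes the phase impossible. In practice the interval at issue runs from 24 h after dosing to the EOT examination on Day 2, and SAP 6.1 already places AEs in that interval in follow-up. Aligning the wording would tidy the text but would change no result.

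The conclusion rests on three assumptions: the termination date is the EOT date, dosing is at about 08:00, and the SAP 6.1 definition governs the programming. The ADS plan was not available to confirm the third. The number of AEs that could fall in the interval cannot be estimated from the documents. The missing 24-hour row is judged from extracted table text, although the rows run without a break to 12:00 and then to EOT.

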7.8.2 Laboratory data

Descriptive statistics will be calculated for screening and post examination visits as well as for the difference from baseline (=screening). The summary statistics will be provided in total.

Laboratory data will be analysed qualitatively via comparison of laboratory data to their reference ranges. Values outside the reference range as well as values defined as clinically relevant will be flagged in the data listings.

Frequency tables of changes with respect to the reference range between screening and post examination will be presented.

Possibly clinically significant abnormal laboratory values are only those identified either in the Investigator's comments on the eCRF or at the RPM/DBLM at the latest. It is the investigator's responsibility to decide whether a lab value is clinically significantly abnormal

or not. Standard or project-specific rules for flagging clinically significant values will not be applied in this study.

The analyses of laboratory data will be based on BI standards [001-MCG-157] ([10](#)).

7.8.3 Vital signs

Descriptive statistics over time and for the changes from baseline will be performed for vital signs (blood pressure and pulse rate) for both formulations together (BI tab + iv).

Section 7.3.3 of the CTP: *For vital signs, the differences from baseline (last value before oral drug administration) will be evaluated.*

In the listing the difference from baseline will also be displayed.

Clinically relevant findings in vital signs will be reported as AEs.

7.8.4 ECG

ECG recordings will be checked by the investigator for pathological results. Clinically relevant abnormal findings for ECG will be listed under 'Relevant Medical History / Baseline Conditions' (when they occurred during screening) or will be reported as adverse events (when they occurred during treatment).

7.8.5 Others

Local tolerability

Local tolerability at the injection site will be assessed by the investigator according to 'swelling', 'induration', 'heat', 'redness', 'pain', or 'other findings'.

A frequency table using the worst assessment will be provided.

10. HISTORY TABLE

Table 10: 1 History table

Version	Date (DD-MMM-YY)	Author	Sections changed	Brief description of change
Final	26-JUN-18		None	This is the final TSAP without any modification
